#### Number of subjects to be enrolled at each center:

- Department of Urology, Zhongda Hospital, Southeast University: 84 cases
- Department of Urology, Nanjing Lishui People's Hospital: 30 cases

- Department of Urology, Wuxi Xishan People's Hospital: 30 cases

**Sample Size:** This study is a prospective, multi-center, randomized, placebo-controlled clinical trial designed to assess the efficacy of early electroacupuncture intervention in improving immediate urinary continence after radical prostatectomy (RP). The Primary Endpoint has been determined as the urine leakage volume (in grams) measured by the 1-hour pad test administered immediately after catheter removal (within the first 1 hour post-removal). This calculation is based on a test comparing two independent sample means. The required parameters include the expected mean difference between groups (effect size,  $\delta$ ), the within-group standard deviation ( $\sigma$ ), the Type I error probability ( $\alpha$ ), and the Type II error probability ( $\beta$ ). We set the two-sided significance level  $\alpha = 0.05$ , statistical power  $(1-\beta) = 0.80$ , and a 1:1 allocation ratio for the two groups (treatment vs. sham acupuncture).

In the absence of a perfectly matched study focusing on post-RP males, comparing electroacupuncture versus sham acupuncture, and using the 1-hour pad test (grams) as the primary endpoint, we have, after rigorous screening, selected a high-quality, large-scale ( $N=504$ ), multi-center randomized controlled trial published by Liu et al. in the Journal of the American Medical Association (JAMA) in 2017 as the primary basis for parameter estimation. That study's methodological design (electroacupuncture vs. sham acupuncture) and primary outcome measure (1-hour pad test leakage volume) are highly consistent with our study, representing the best available evidence. Although its study population was women with stress urinary incontinence, we consider its reported effect size and variability data to be the most reasonable reference for this calculation, given the cross-gender commonality of the core physiological mechanism (sacral neuromodulation via electroacupuncture) for regulating urinary control.

Based on the results from Liu et al.'s study:

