- **Expected Effect Size ( $\delta$ ):** The electroacupuncture group showed 7.4 grams more reduction in 1-hour pad test leakage compared to the sham acupuncture group. We use this as the expected mean difference between groups.
- **Within-group Standard Deviation ( $\sigma$ ):** Based on the reported 95% confidence interval of the effect size, we extrapolated the pooled standard deviation for the "change value" in leakage volume (before and after intervention) to be approximately 14.9 grams.

Based on the parameters above, using the sample size formula for comparing two independent means:  $n = [(Z\alpha/2 + Z\beta)^2 \times 2\sigma^2] / \delta^2$

The calculation shows that to achieve 80% power, **each group requires at least 64 subjects.**

Considering the short intervention cycle and clear follow-up nodes of this study, we estimate a dropout or withdrawal rate of approximately 10%. To compensate for this potential sample loss, the adjusted number of recruits needed per group is  $64 / (1 - 0.10) \approx 71.11$ . Rounding up, we determine that **each group needs to recruit 72 subjects**.

In summary, this study plans to enroll a total of **144 subjects** (72 in the treatment group, 72 in the control group). This sample size is sufficient to statistically and effectively test the core hypothesis of this study and is feasible within the multi-center collaborative framework. An interim analysis will assess whether the sample size needs adjustment based on actual enrollment and data variability.

**Reference:** Liu Z, Liu Y, Xu H, et al. Effect of Electroacupuncture on Urinary Leakage Among Women With Stress Urinary Incontinence: A Randomized Clinical Trial. *JAMA*. 2017;317(24):2493–2501. doi:10.1001/jama.2017.7220

**(3) Study Period** 2025.08.01——2027.08.01

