### Outcome Measures

Follow-up on patient's urinary continence at 1 week, 4 weeks, 8 weeks, 12 weeks, and 24 weeks after catheter removal (half-year follow-up).

1. **Primary Endpoint:** Urine leakage volume (grams) measured by the first 1-hour pad test during the follow-up at 1 week post-catheter removal.
2. **1-hour Pad Test Results:** Conducted at the 4-week and 24-week follow-ups.
3. **ICIQ-SF Questionnaire Score:** At 1, 4, 8, 12, and 24 weeks post-removal to evaluate incontinence symptoms and their impact on quality of life. The proportion of completely continent patients (zero leakage) will directly quantify immediate continence.
4. **Self-Rating Anxiety Scale (SAS) Score:** To assess the potential improvement in patients' psychological state due to the acupuncture intervention.
5. **Voiding Diary and IPSS:** Patients will maintain a voiding diary and complete the International Prostate Symptom Score (IPSS) questionnaire at each follow-up node to assess nocturia and provide a comprehensive evaluation of urinary function.

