## (7) Treatment Methods

All patients will have their urinary catheter removed on postoperative day 14 (POD14). The early electroacupuncture intervention (including real electroacupuncture and sham electroacupuncture) will be initiated on postoperative day 7 (POD 7), with subsequent sessions on POD 9 and POD 11, for a total of 3 sessions.

**Treatment Group:** Receive electroacupuncture at acupoints including Shenshu (BL23), Pangguangshu (BL28), and Baliao (BL31-34), 30 minutes each time. A continuous wave of 2Hz will be used initially, with the intensity gradually increased to a level that is comfortable for the patient. The current intensity will be 1-5mA and can be gradually increased to the maximum tolerable level for the patient.

**Control Group:** Will use non-invasive sham acupuncture needles: validated blunt-tip, non-penetrating needles (such as Park or Streitberger needles). When pressure is applied, the needle tip retracts into the handle, giving the patient a sensation of pressure on the skin, but it does not puncture the skin. The procedure will be performed at **non-acupoints** (points 1-2 cm away from the real acupoints but not on the same meridian). The electroacupuncture device clips will also be attached to the sham needle handles, and the device will be turned on (emitting the same sound or light indicators), but **no electrical current will be delivered**. This ensures the entire treatment scenario is visually and auditorily identical to the real treatment group.

To ensure all subjects receive consistent standard postoperative rehabilitation guidance and to control for potential confounding variables, all successfully enrolled

patients (regardless of group) will receive standardized Pelvic Floor Muscle Training (PFMT) health education on POD 7 (the same day as the first intervention).

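### The 80% power rests on the SD of a before-after change, but the primary endpoint is a single pad weight after catheter removal, whose SD the protocol does not support

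*Protocol*

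**What the plan says.** The Sample Size paragraph (Study Content, item 2) plans a two-group comparison: "This calculation is based on a test comparing two independent sample means". Its inputs are a two-sided alpha of 0.05, power of 0.80, 1:1 allocation, and a difference and SD taken from one published trial of electroacupuncture against sham.

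- Difference: "The electroacupuncture group showed 7.4 grams more reduction in 1-hour pad test leakage compared to the sham acupuncture group".
- SD: extrapolated from that trial's confidence interval as the pooled SD of the change "in leakage volume (before and after intervention) to be approximately 14.9 grams".
- Result: "The calculation shows that to achieve 80% power", 64 subjects per group are needed. With 10% dropout this becomes 72 per group, 144 in total.

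The primary endpoint is one pad weight. The Sample Size paragraph has it "administered immediately after catheter removal (within the first 1 hour post-removal"; Outcome Measures and Efficacy Evaluation have it "measured by the first 1-hour pad test during the follow-up at 1 week post-catheter removal". These times conflict, which is a separate matter, but each version is a single weight.

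On the schedule, Treatment Methods states: "All patients will have their urinary catheter removed on postoperative day 14 (POD14". The three sessions fall on POD 7, 9 and 11.

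**The concern.** The formula for two independent means needs the between-patient SD of the variable that will be compared. Here that is the single pad weight. The figure entered is labelled as the SD of a different quantity, a within-patient change, which this trial cannot observe: patients enter one week after surgery with a catheter in place, and treatment ends before the catheter comes out.

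A change SD may be larger or smaller than the SD of a single weight, depending on how strongly the before and after values correlate. The protocol nevertheless gives 80% without condition, calls 144 sufficient, and under Clinical Operational Feasibility calls the number statistically reasonable. At stake is whether a reader, an ethics committee or a funder can rely on that 80%.

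**Working it through.** **Step 1. Reproduce the plan's figure.** Inputs from the Sample Size paragraph: difference 7.4 g, SD 14.9 g, two-sided alpha 0.05, power 0.80.

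n = (1.960 + 0.842)² × 2 × 14.9² / 7.4² = 7.849 × 444.02 / 54.76 = 63.6, so 64 per group.

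64 / 0.90 = 71.1, so 72 per group and 144 in total. Power at 64 per group is 80.2% by the normal formula and 79.6% by the t-test. The arithmetic is right; the question is what the 14.9 g measures.

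**Step 2. Look for an SD of the single weight.** The protocol has none.

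- The Rationale gives a mean daily leakage of 408.0 mL in the first week after removal. This is a 24-hour mean without an SD.
- The preliminary experiment in 15 patients reports only ICIQ-SF scores.
- The sample size text gives only the change SD.

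**Step 3. Link the two SDs.** Assume that the source trial had the same SD before and after treatment, with correlation ρ between the two. Then

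SD of change = SD of single weight × √(2(1 − ρ)), so SD of single weight = 14.9 / √(2(1 − ρ)).

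The two are equal only when 2(1 − ρ) = 1, that is at ρ = 0.5. Power is by t-test at 64 evaluable per group for 7.4 g:

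| Assumed ρ | √(2(1 − ρ)) | SD of single weight | Power |
|---|---|---|---|
| 0.3 | 1.183 | 12.6 g | 91% |
| 0.5 | 1.000 | 14.9 g | 80% |
| 0.7 | 0.775 | 19.2 g | 58% |
| 0.8 | 0.632 | 23.6 g | 42% |

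The documents do not give ρ, so every row is an assumption. The table covers only the change-to-single-weight step within the source population. The SD in men just after catheter removal may differ further, in either direction.

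**Step 4. Check the 7.4 g separately.** Under randomisation the expected difference in change equals the expected difference in post-treatment means. The change scale alone therefore does not invalidate the difference. Its transfer from women already leaking to men treated before leakage can occur remains an assumption.

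**The case against.** The protocol is open about its borrowing. It says that no matched study was found, acknowledges the population ("Although its study population was women with stress urinary incontinence"), argues for a shared mechanism, notes that the source used the same 1-hour pad test, and labels its SD as a change value. That is a fair defence of the choice of source trial, and it stands. It does not reach the narrower point: nothing is said about using a change SD for a single weight, and a shared mechanism says nothing about how widely pad weights vary between patients.

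The mismatch may also cost nothing. At a correlation of 0.5 the two SDs agree, and below it the change SD is the larger and the plan is conservative. This stands too. A reader might infer from the lower rows of the table that the trial is underpowered. The documents do not support that, because they give neither the correlation nor an SD for the endpoint.

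Finally, the protocol plans an interim look at whether the sample size needs adjusting for data variability. Since no change score exists in this trial, such a check could only use the single weight, so the plan is not blind to the problem. Details of the estimator may sit in an SAP that is not shown. The interim look may correct N later, but it does not make the present 80% a supported figure.

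**Conclusion.** The point holds as a defect in the stated justification. The 80% depends on a change SD standing in for the SD of a single post-removal weight, and the protocol gives no ground for that substitution. The size of the error cannot be fixed from the documents. Under equal SDs before and after, correlations from 0.3 to 0.8 correspond to power from 91% down to 42%, with 80% at 0.5. The conclusion holds for either stated time of the primary endpoint. It is a point to correct in the protocol, and it gives no basis for a larger or a smaller trial.

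**What to change.** Keep N at 144, since there is no SD on which to re-size, and make three changes to the Sample Size paragraph.

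1. Replace the power statement with a conditional one: *64 evaluable subjects per group give about 80% power for a 7.4 g difference only if the between-patient SD of the single 1-hour pad weight, at the primary time point, is about 14.9 g or less.* Follow it with the range of SDs and powers above. The time point must first be reconciled between the Sample Size paragraph and Outcome Measures / Efficacy Evaluation, because the SD may differ between the first hour and one week.
2. State that 14.9 g is a change-score SD from the source trial, and that both it and 7.4 g are assumptions for this endpoint and population.
3. State that the interim sample size check uses the blinded pooled SD of the primary pad weight, with no comparison between arms. Pooling over both arms adds little: if the true difference is 7.4 g and the within-group SD 14.9 g, the pooled value is √(14.9² + 3.7²) = 15.4 g.

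The cost is wording, plus a power claim that becomes conditional and may look less favourable. The interim SD will be imprecise. From 72 evaluable patients (half of 144, an assumption) its 95% interval runs from about 14% below to 20% above the estimate (chi-square, 71 degrees of freedom, normality assumed). It would probably be wider if pad weights are skewed, which is plausible since the protocol expects some patients with zero leakage. The check may point to more patients or to fewer.

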### Study Subject Sampling and Allocation Method

This study will employ a prospective, multi-center, randomized controlled trial design. All patients undergoing radical prostatectomy during the study period who meet all inclusion criteria, do not meet any exclusion criteria, and voluntarily sign the informed consent form will be enrolled consecutively. To ensure the scientific rigor of the allocation process, subject allocation will utilize a **centralized, stratified block randomization** method. We will use participating hospitals as the stratification factor, generating independent random sequences for each center to eliminate potential inter-institutional bias. Within each stratum, we will use mixed block sizes (sizes 4 and 6) for random allocation to maintain a close dynamic balance between the treatment and control groups at all stages of the study. To achieve allocation concealment, the random sequences will be generated by an independent statistician (not involved in clinical work) and deployed within a secure central randomization system. On-site researchers will only be able to obtain the patient's group assignment through the system *after* the patient is formally enrolled, thereby preventing selection bias. This study plans to randomly allocate a total of 144 subjects to the treatment group and the control group in a 1:1 ratio.

### Informed Consent of Study Subjects

Signing of the informed consent form.

### Outcome Measures

Follow-up on patient's urinary continence at 1 week, 4 weeks, 8 weeks, 12 weeks, and 24 weeks after catheter removal (half-year follow-up).

1. **Primary Endpoint:** Urine leakage volume (grams) measured by the first 1-hour pad test during the follow-up at 1 week post-catheter removal.
2. **1-hour Pad Test Results:** Conducted at the 4-week and 24-week follow-ups.
3. **ICIQ-SF Questionnaire Score:** At 1, 4, 8, 12, and 24 weeks post-removal to evaluate incontinence symptoms and their impact on quality of life. The proportion of completely continent patients (zero leakage) will directly quantify immediate continence.
4. **Self-Rating Anxiety Scale (SAS) Score:** To assess the potential improvement in patients' psychological state due to the acupuncture intervention.
5. **Voiding Diary and IPSS:** Patients will maintain a voiding diary and complete the International Prostate Symptom Score (IPSS) questionnaire at each follow-up node to assess nocturia and provide a comprehensive evaluation of urinary function.

## (7) Treatment Methods

All patients will have their urinary catheter removed on postoperative day 14 (POD14). The early electroacupuncture intervention (including real electroacupuncture and sham electroacupuncture) will be initiated on postoperative day 7 (POD 7), with subsequent sessions on POD 9 and POD 11, for a total of 3 sessions.

**Treatment Group:** Receive electroacupuncture at acupoints including Shenshu (BL23), Pangguangshu (BL28), and Baliao (BL31-34), 30 minutes each time. A continuous wave of 2Hz will be used initially, with the intensity gradually increased to a level that is comfortable for the patient. The current intensity will be 1-5mA and can be gradually increased to the maximum tolerable level for the patient.

**Control Group:** Will use non-invasive sham acupuncture needles: validated blunt-tip, non-penetrating needles (such as Park or Streitberger needles). When pressure is applied, the needle tip retracts into the handle, giving the patient a sensation of pressure on the skin, but it does not puncture the skin. The procedure will be performed at **non-acupoints** (points 1-2 cm away from the real acupoints but not on the same meridian). The electroacupuncture device clips will also be attached to the sham needle handles, and the device will be turned on (emitting the same sound or light indicators), but **no electrical current will be delivered**. This ensures the entire treatment scenario is visually and auditorily identical to the real treatment group.

To ensure all subjects receive consistent standard postoperative rehabilitation guidance and to control for potential confounding variables, all successfully enrolled

patients (regardless of group) will receive standardized Pelvic Floor Muscle Training (PFMT) health education on POD 7 (the same day as the first intervention).

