##### **Subject Exclusion Criteria are as follows:**

1. Pathology report shows positive surgical margins.
2. Has undergone treatment for postoperative urinary incontinence, such as cystostomy, urinary sphincter reconstruction, or urethral sling surgery.
3. Currently receiving or has received treatments with similar principles to acupuncture (e.g., electroacupuncture, moxibustion, warm needling) within the past six months.
4. Patients with urinary tract infections (excluding asymptomatic lower urinary tract infections).
5. Known severe cardiac diseases, such as severe arrhythmia, severe cardiac insufficiency, acute myocarditis, constrictive pericarditis, cardiac tamponade, or severe valvular disease.
6. Known liver damage or potential severe liver disease (ALT or AST  $> 10$  times normal).
7. Known severe renal impairment (eGFR  $< 25$  mL/min/1.73m^2), or planning/undergoing dialysis, or acute contrast-induced nephropathy at screening.
8. Known severe primary diseases in other vital organs or the hematopoietic system.
9. Known coagulation dysfunction (with typical clinical diagnosis or definitive laboratory test results).
10. Patients with psychiatric disorders or cognitive impairment; severe depression, alcohol dependence, or history of drug abuse.

11. Existing urinary incontinence due to other reasons.
12. Patients deemed unsuitable for the study by the investigator, or those with a high probability of dropping out, such as frequent changes in work environment leading to difficulty in follow-up.
13. Life expectancy  $\leq 6$  months, as judged by the investigator.
14. Currently participating in other clinical trials.

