### (3) Enrollment and Treatment Protocol

Information on patients who have undergone radical prostatectomy will be obtained from the EMR systems of Zhongda Hospital, Nanjing Lishui People's Hospital, and Wuxi Xishan People's Hospital. After screening patients who meet the inclusion/exclusion criteria and signing the informed consent form, patients will be allocated into groups using a centralized, stratified block randomization method and receive either acupuncture treatment or sham acupuncture treatment.

**Trial Treatment Protocol:** All patients will have their urinary catheter removed on postoperative day 14 (POD 14). The early acupuncture intervention (including real and sham acupuncture) will be initiated on postoperative day 7 (POD 7), with subsequent sessions on POD 9 and POD 11, for a total of 3 sessions.

**Treatment Group:** Receive electroacupuncture at acupoints including Shenshu (BL23), Pangguangshu (BL28), and Baliao (BL31-34), 30 minutes each time. A continuous wave of 2Hz will be used initially, with the intensity gradually increased to a level that is comfortable for the patient. The current intensity will be 1-5mA and can be gradually increased to the maximum tolerable level for the patient.

**Control Group:** Will use non-invasive sham acupuncture needles: validated blunt-tip, non-penetrating needles. When pressure is applied, the needle tip retracts into the handle, giving the patient a sensation of pressure on the skin, but it does not puncture the skin. The procedure will be performed at **non-acupoints** (points 1-2 cm away from the real acupoints but not on the same meridian). The electroacupuncture device clips will also be attached to the sham needle handles, and the device will be turned on (emitting the same sound or light indicators), but **no electrical current will be delivered**. This ensures the entire treatment scenario is visually and auditorily identical to the real treatment group.

To ensure all subjects receive consistent standard postoperative rehabilitation guidance and to control for potential confounding variables, all successfully enrolled patients (regardless of group) will receive standardized Pelvic Floor Muscle Training (PFMT) health education on POD 7 (the same day as the first intervention).

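### The active current is set by what the patient feels, while the sham has no current and no matching titration step, so the sham cannot be relied on to mask patients, and perceived allocation is never asked.

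*Protocol*

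**What the plan says.** The procedure appears twice in the Protocol, under (7) Treatment Methods and (3) Enrollment and Treatment Protocol, in nearly the same words.

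- **Active arm.** Stimulation starts as a 2 Hz continuous wave, "with the intensity gradually increased to a level that is comfortable for the patient". The current range is 1-5 mA, and it "can be gradually increased to the maximum tolerable level for the patient". Under either description, the patient's sensation sets the end point.
- **Sham arm.** A blunt retracting needle is used 1-2 cm away from the real points, "giving the patient a sensation of pressure on the skin, but it does not puncture the skin". The device is clipped on and shows the same lights or sounds, but "no electrical current will be delivered". No imitation of the intensity adjustment is described.
- **Stated result.** "This ensures the entire treatment scenario is visually and auditorily identical to the real treatment group".

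The sample-size paragraph labels the design: "This study is a prospective, multi-center, randomized, placebo-controlled clinical trial". The text at hand does not say who is masked. Study Subject Sampling and Allocation Method covers concealment of the sequence up to enrolment only. Outcome Measures, Efficacy Evaluation and (4) Statistical Analysis contain no question on perceived allocation.

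**The concern.** Sight and sound are not the channels most likely to tell a man which arm he is in. One group feels a current, and someone adjusts it to what they can comfortably bear. The other group feels pressure and, as written, goes through no adjustment. A man who has been told that real and sham treatments exist could draw a conclusion from either experience.

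ICIQ-SF, the Self-Rating Anxiety Scale, IPSS and the voiding diary are reported by the patient and can respond directly to what he believes he received. The 1-hour pad test is weighed, which protects it in part. But every man is taught pelvic floor muscle training on POD 7, and how hard he practises, or how he performs the test, may depend on his belief. Either route would enter the group difference and be read as an effect of electroacupuncture over placebo.

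If nobody asks the men, nobody can later say how well the sham worked. A statistical analysis plan cannot repair this, because the answer has to be collected during the trial.

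**Working it through.** **1. The arms side by side, from (7) Treatment Methods and (3) Enrollment and Treatment Protocol**

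| What the patient can perceive | Active | Sham | Matched? |
|---|---|---|---|
| Device lights and sounds | on | on | yes, as stated |
| Pressure at the skin | needle | blunt needle | imitated |
| Skin penetration | yes | no | no |
| Electrical sensation | 1-5 mA | none | no |
| Adjustment of intensity to sensation | described | not described | no |

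The sentence on identity covers the first row. The needle design addresses the second. Nothing in the protocol addresses the last two.

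**2. Is there a check elsewhere?** Outcome Measures and Efficacy Evaluation list the pad test, ICIQ-SF, anxiety scale, diary and IPSS. (4) Statistical Analysis covers ITT, normality, ANCOVA, multiple imputation and a subgroup by incontinence type. None mentions perceived allocation. Clinical Operational Feasibility mentions standardized training, and the section on the team's earlier work mentions supervision of both procedures. Neither describes a dummy titration.

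**3. The plan's own figure.** Inputs from the sample-size section: difference 7.4 g, SD 14.9 g, two-sided alpha 0.05, power 0.80, 1:1 allocation.

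n = 2 × 14.9² × (1.960 + 0.842)² / 7.4² ≈ 63.6, so 64 per group. Power at 64 is 80.2%. With 10% dropout, 64 / 0.90 = 71.1, so 72. The stated sample size reproduces, and this point does not affect it.

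**4. Illustration of what is at stake.** Assume no true effect, and let unmasking alone shift the mean difference by b grams. The documents give no value for b, so this shows sensitivity only and does not estimate the bias.

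SE = 14.9 × √(2/64) = 2.634 g. The chance of a significant result is 1 − Φ(1.96 − b/SE) + Φ(−1.96 − b/SE).

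| Assumed b | b/SE | False-positive rate |
|---|---|---|
| 0 g | 0 | 5.0% |
| 1 g | 0.38 | 6.7% |
| 2 g | 0.76 | 11.8% |
| 3 g | 1.14 | 20.7% |

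**The case against.** The strongest reply is that the quoted sentence is literally about sight and sound and claims nothing about electrical sensation. A no-current sham is also a legitimate choice, and the protocol never uses the word double-blind. All of that stands: this is a limitation of the design as written, not a false statement or a contradiction. But the sentence and the pressure needle are the only patient masking described, and the placebo-controlled label depends on them.

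The second reply is that the primary endpoint is a weight. Outcome Measures places it 1 week after removal, which is POD 21 and ten days after the last session on POD 11. (The sample-size paragraph places it in the first hour after removal; this point does not depend on which applies.) This also stands in part: the pad test is less exposed than the questionnaires.

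The third is that a script may exist in training material, or a statement to patients in the consent form, which is not part of the text reviewed. That is possible, but the treatment sections should still require it.

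A reader might also infer more than the text supports:

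- **That masking fails.** There are no blinding data. The procedure shows only that masking cannot be relied on.
- **That only sight and sound are imitated.** Skin pressure is imitated too.
- **That titration happens at every one of the three sessions.** The protocol does not say whether intensity rises within or across sessions.
- **That previously treated men will recognise the missing current.** The exclusion "Currently receiving or has received treatments with similar principles to acupuncture" is limited to the past six months, so men with older experience may enter. How many will do so, and what they would notice, is not known.

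**Conclusion.** The point holds in a limited form. As written, the sham matches sight and sound and imitates skin pressure, but not electrical sensation or the adjustment of intensity. It cannot be relied on to mask patients, and the trial collects nothing that would show whether it did. The risk is greatest for ICIQ-SF, the anxiety scale, IPSS and the diary, and smaller but possible for the pad test.

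No gram figure for the bias should be claimed. A reader might multiply a guessed share of unmasked men by a guessed shift and compare the result with 7.4 g, but neither factor is in the documents. The 7% to 21% range rests on an assumed shift of 1 to 3 g, no true effect, the protocol's SD of 14.9 g and 64 men per group.

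Nor should a precision claim be attached to the guess question. A half-width of about 12 percentage points (1.96 × √(0.25/64) = 0.1225) applies to a yes/no proportion near one half. With a don't-know option, one half is no longer the chance benchmark.

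**What to change.** None of these steps changes the current, the points or the sessions.

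1. In (7) Treatment Methods and (3) Enrollment and Treatment Protocol, require one scripted titration procedure for both arms: the same dial movements, the same questions, and the same prior statement that stimulation may or may not be felt. Each arm's output stays as already specified. This removes the difference in the exchange, though not the difference in sensation.
2. After the POD 11 session and before catheter removal on POD 14, ask every man which treatment he believes he received: real, sham or don't know. Report the answers descriptively by arm beside the results. Asking before removal keeps his continence after removal from influencing the answer.
3. Qualify the sentence on identity in both sections to say that sight and sound are matched and electrical sensation is not.

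The cost is a short operator script, one question on the case report form, one descriptive table and a wording amendment. The downside is that the answers may show imperfect masking and temper the claim. The question should be added early, since it cannot be asked usefully of men who are already past catheter removal.
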